## GLOSSARY OF ABBREVIATIONS

[figure not shown]
6MWT	6 –minute walk test
AE	Adverse event
AR	Adverse reaction
BP	Blood pressure
bpm	Beats per minute
CAMPHOR	Cambridge Pulmonary Hypertension Outcome Review
CMR	Cardiac Magnetic Resonance
CPET	Cardiopulmonary exercise test
CRF	Case Report Form
FPPV	First patient first visit
GCP	Good Clinical Practice
HIV	Human Immunodeficiency Virus
ICF	Informed Consent Form
ICH	International Conference on Harmonisation
IMP	Investigation Medicinal Product
IPAH	Idiopathic pulmonary arterial hypertension
i.v.	Intravenous
LPLV	Last patient last visit
NT pro-BNP	N-terminal pro-brain natriuretic peptide
NYHA	New York Heart Association
PAH	Pulmonary arterial hypertension
PAP	Pulmonary arterial pressure
PCWP	Pulmonary capillary wedge pressure
PH	Pulmonary hypertension
PVR	Pulmonary vascular resistance
RA	Regulatory Authority
REC	Research Ethics Committee
RHC	Right heart catheterisation
SAE	Serious Adverse Event
SAR	Serious Adverse Reaction
SmPC	Summary of Product Characteristics
SOP	Standard Operating Procedure
SPM	Study Procedures Manual (study specific SOP binder)
sTfR	Soluble transferrin receptor
SUSAR	Suspected Unexpected Serious Adverse Reaction
SVR	Systemic vascular resistance
WHO	World Health Organisation

## Study Summary

TITLE	What is the effect of intravenous iron supplementation on exercise capacity and quality of life in patients with idiopathic pulmonary arterial hypertension (IPAH) and iron deficiency?
PHASE	II
DESIGN	Multi-centre, double-blind, randomised, placebo-controlled, crossover study
OBJECTIVES	To assess the clinical value of using intravenous iron (ferric carboxymaltose) infusion (Ferinject®) in iron deficient patients with IPAH.
OUTCOME MEASURES	
Primary:
 
 
• Endurance time at the end of endurance bicycle cardiopulmonary exercise testing at 80% peak work rate determined from the incremental exercise test
 
 
Secondary:
 
 
• Incremental bicycle cardiopulmonary exercise testing - peak VO2 (ml/min/kg), VO2 at metabolic threshold, VE/VCO2 slope, VO2/WR slope and O2 pulse.
 
• VO2 at the end of endurance bicycle cardiopulmonary exercise testing at 80% peak work rate determined from the incremental exercise test
 
• Gas exchange at 3 minutes after the start of the work phase of an endurance exercise test at 80% peak work rate determined from the incremental exercise test
 
• Iron indices – serum iron, transferrin saturations, ferritin, soluble transferrin receptor (sTfR), unsaturated iron binding capacity (UIBC), red cell distribution width (RDW) and erythropoietin (EPO) levels
 
• 6 minute walk distance and Borg dyspnoea scale
 
• NYHA WHO functional class
 
• NT-pro-BNP
 
• Quality of life (CAMPHOR questionnaire) and the self-reported Patient Global Assessment
 
• Safety - the occurrence of adverse events
 
• Cardiac MRI - right ventricular volumes, mass, ejection fraction, stroke volume and diastolic function (at sites where facility is available)
 

POPULATION	An estimated 60 patients will be enrolled.
STUDY CENTRES	5 centres in UK/EU.
STUDY DURATION	
FPPV: Q4 2011
 
LPLV: Q4 2017

ELIGIBILITY	
Inclusion criteria
 
 
1. Males or females aged between 16–75 years old
 
2. PAH which is idiopathic, heritable or associated with anorexigens.
 
3. Iron deficiency as defined by any one of the following criteria: sTfR levels > 28.1 nmol/l (where sTfR analysis is available) or one of the following: Ferritin < 37 ug/l; transferrin saturations < 16.4%; iron < 10.3 umol/l.
 
4. Documented diagnosis of PAH by right heart catheterisation performed at any time prior to Screening showing: resting mean pulmonary artery pressure >25mmHg, pulmonary capillary wedge pressure =/ < 15 mm Hg and normal or reduced cardiac output;
 
5. 6 minute walking distance greater than 50m at entry;
 
6. Stable on an unchanged PAH therapeutic regime (any combination of endothelin receptor antagonist, phosphodiesterase inhibitor or prostacyclin
 

	
analogue) for at least 1 month.
 
7. Able to provide written informed consent prior to any study-mandated procedures
 
8. Female subjects of child-bearing potential are eligible to participate if they agree to use one of the following contraception methods:
 
 
• Combined (estrogen and progestogen containing) hormonal contraception associated with inhibition of ovulation: 
 
○ oral
 
○ intravaginal
 
○ transdermal
 
 
 
• Progestogen-only hormonal contraception associated with inhibition of ovulation: 
 
○ oral
 
○ injectable
 
○ implantable
 
 
 
• Intrauterine device (IUD)
 
• Intrauterine hormone-releasing system (IUS)
 
• Bilateral tubal occlusion
 
• Vasectomised partner
 
• Sexual abstinence
 
 
Exclusion criteria
 
 
1. Unable to provide informed consent.
 
2. Clinically-significant renal disease (Creatinine clearance < 30 ml/min per 1.73 m^2 calculated from CKD-Epi http://www.qxmed.com/renal/Calculate-CKD-EPI-GFR.php) or liver disease (including serum transaminases > 3 times upper limit of normal).
 
3. Haemoglobin concentration <10 g/dl.
 
4. Patients will be excluded if any single parameter (iron, ferritin or transferrin saturation) exceeds 1x upper limit of normal (ULN) in the local lab reference range.
 
5. Patients with moderate to severe hypophosphatemia as defined as <0.65mmol/L
 
6. Known to have haemoglobinopathy e.g. sickle cell disease, thalassaemia.
 
7. Admission to hospital related to PAH or change in PAH therapy within 1 month prior to Screening.
 
8. Evidence of left ventricular disease or significant lung disease on high-resolution CT scanning or lung function as judged by the investigator
 
9. Acute or chronic infection or inflammation.
 
10. Significant uncontrolled asthma as judged by the investigator, eczema or atopic allergies.
 
11. Females who are lactating or pregnant.
 
12. Individuals known to have HIV, Hepatitis B or C or Creutzfeld-Jakob disease.
 
13. Known hypersensitivity to Ferinject® or any of its excipients and any other iron supplement preparation.
 
14. Evidence of disturbances in utilisation of iron.
 
15. Significant blood loss (e.g. GI bleed) within the last 3 months or history of menorrhagia.
 

--	---

	
16. Unable to perform a Cardiopulmonary Exercise Test i.e. due to syncope or musculoskeletal factors.
 
17. Patients who have received an investigational medicinal product within 30 days of entering the baseline visit

TREATMENT	
All the study participants will attend a screening visit, two treatment periods at Week 0 and Week 12, telephone visits at Week 2 and Week 14 and a follow up visit at Week 24 to evaluate the kinetics of iron re-depletion.
 
Potential participants will be screened using data collected during their routine outpatient appointment at the Pulmonary Hypertension Service. Any unavailable or missing data will be collected at the baseline visit (week 0) once the patient has provided written informed consent.
 
Eligible participants will be admitted to the research unit for up to 3 days in order to complete the Baseline (Week 0) assessments including a physical examination, medical history, ECG, bloods to assess routine haematology and clinical chemistry and measure biomarkers, 6-Minute Walk Test, CAMPHOR questionnaire and incremental and endurance cardiopulmonary exercise tests (CPET).
 
As outlined in Figures 1, following completion of the Baseline assessments at Week 0 patients will be randomly allocated 1:1 to receive an infusion of either Ferinject® or saline.
 
At Week 2, participants will attend a phone call from the research unit for a follow up visit. This will include any AE or medication and PGA questionnaire.
 
At Week 12 all participants will be admitted to the research unit for up to 3 days to repeat the assessments done at Baseline (Week 0). Following completion of the Week 12 procedures, the patients will be switched to the other treatment arm (i.e. those who received Ferinject® at baseline will be administered a saline infusion, and vice versa).
 
Thereafter participants will have a telephone follow up assessments at Weeks 14. The assessments at these visits are the same as for Week 2.
 
Participants will have a final hospital follow up visit at Week 24 during which the assessments will be the same as those performed at baseline and Week 12.
 
At selected centres participants will be given the option to undergo additional cardiac MRI (Weeks 0, 12 and 24).
 
At the Sheffield site only, if participants agree, they will have two extra blood samples taken (50 ml extra in total) to assess neutrophil and peripheral blood mononuclear cell function and expression at Week 0 and 2 or Week 0 and 12 of study participation.


**Figure 1** – Schematic overview of study to determine the effect of intravenous iron supplementation on cardiopulmonary haemodynamics and exercise capacity in iron deficient patients with IPAH.

## 1. BACKGROUND AND RATIONALE

Iron deficiency in the absence of anaemia is now well documented in patients with idiopathic pulmonary arterial hypertension, IPAH (1-3). Estimates suggest a prevalence of 43 to 60% and it is associated with poor survival (1). Oral iron replacement has been explored as a treatment by Ruiter et al (2011) with only limited response in 44% of patients, consistent with impaired absorption of oral iron from the gut from raised hepcidin levels (1), and the authors conclude that a trial of intravenous iron therapy is required. Ruiter et al (2015) have treated 15 patients with ferric carboxymaltose (Ferinject®) given as a single infusion and demonstrated restoration of serum iron levels (4). Viethen et al (2013) have treated 20 patients, again through a single infusion of 1000mg over 15min of ferric carboxymalose (Ferinject®), and successfully restored serum iron (5). The authors conclude “that parenteral iron supplementation with ferric carboxymaltose ... is well tolerated in patients with PAH and iron deficiency”. But as these studies were open-label, a double-blind proof-of-concept study is essential to help decide on the future use of intravenous ferric carboxymaltose (Ferinject®) in IPAH. This study will establish whether iron supplementation has clinical benefit. If there is no evidence of improvement, only a small patient population has been exposed and costs are kept to a minimum. If the data support a potentially useful therapeutic effect and suggest this drug is safe, the study will be used to power a Phase 3 study to address efficacy.

A 24-week double-blind, randomised, placebo-controlled, crossover study will investigate whether a single dose of 1g of Ferinject® improves exercise capacity and quality of life and is well-tolerated. This is a multicentre study. All patients will be followed for up to 24 weeks after dosing with Ferinject® to measure the kinetics of iron re-depletion.

Patients with IPAH and iron-deficiency, who have been stable on their current therapy for the preceding 1 month, will be treated with 1000 mg or 15 mg/kg (whichever is the smaller) Ferinject® in line with the Summary of Product Characteristics (SmPC) and clinical experience with the product. Soluble transferrin receptor (sTfR) is the best measure of iron deficiency in inflammatory diseases such as IPAH ( $>28.1 \text{ nmol/l}$ ). Where available, sTfR levels will be used as the screening tool to assess iron deficiency and inclusion in to the study. But as it is not routinely available at all participating centres, iron deficiency will also be defined by standard laboratory measures of ferritin  $< 37 \text{ ug/l}$ , iron  $< 10.3 \text{ umol/l}$  or transferrin saturations  $< 16.4\%$ . Using these criteria, modelling of data from our previous work (1) show that 83% of patients will have raised sTfR levels  $> 28.1 \text{ nmol/l}$ .

A formula exists to guide the amount of iron replacement required to render patients with anaemia iron-replete. This is based on the difference between current and target haemoglobin. In IPAH, this formula is likely to be inappropriate since the target haemoglobin is not known as patients may be hypoxaemic and thus require higher levels of haemoglobin. Indeed, many patients with iron deficiency have normal haemoglobin levels, but increased circulating EPO levels, implying an ongoing drive to increased red cell mass. Patients in the FERRIC-HF trial of iron supplementation in congestive heart failure were defined as having iron deficiency if ferritin was less than 100 ug/l or between 100 and 300 ug/l with transferrin saturations  $< 20\%$  (6). By 4 and 16 weeks,  $781 \pm 94$  and  $1269 \pm 297$  mg iron sucrose had been given to the non-anaemic group ( $\text{Hb} > 12.5 \text{ g/dl}$ ) and  $1051 \pm 219$  and  $1583 \pm 366$  mg had been given to the anaemic group. Iron sucrose can be given in doses up to 200mg, whereas Ferinject® can be given in doses up to 1000mg due their differing pharmacokinetics. We will give a single 1000mg (or 15 mg/kg) dose to answer whether this simple strategy is of benefit and well-tolerated. Experience from Viethen et al (2013) and Ruiter et al (2015) in a total of 35 patients indicate that this is well tolerated and does not lead to iron overload (4,5). Using full iron profiling we will be able to determine how long this dose maintains iron repletion.

Ferinject® has recently been used in a large phase III trial in heart failure (7). Adverse events were few in 304 patients assigned to receive Ferinject® and were not significantly different from the placebo group (n=105). Only 2 patients reported injection site pain and no allergic reactions were described.

## **2. STUDY OBJECTIVES**

To assess the clinical value of using intravenous iron (Ferinject®) infusion in iron deficient patients with IPAH.

## **3. STUDY OUTCOME MEASURES**

### **3.1. Primary outcome**

Endurance time at the end of endurance bicycle cardiopulmonary exercise testing at 80% peak work rate determined from the incremental exercise test.

### **3.2. Secondary outcomes:**

The secondary outcomes will be measured by capturing other data, particularly exercise parameters and NT-pro-BNP data.

A summary of the measurements that will be made is as follows:

- Incremental bicycle cardiopulmonary exercise testing – measurements will include peak VO2 (ml/min/kg), VO2 at metabolic threshold, VE/VCO2 slope, VE/VCO2 equivalents at metabolic threshold, VO2/WR slope and O2 pulse. Details are described in the Study Procedures Manual (SPM).
- VO2 at the end of endurance bicycle cardiopulmonary exercise testing at 80% peak work rate determined from the incremental exercise test
- Gas exchange at 3 minutes after the start of the work phase of an endurance exercise test at 80% peak work rate determined from the incremental exercise test
- Iron indices – serum iron, transferrin saturations, ferritin, soluble transferrin receptor, RDW, EPO, and UIBC
- 6 minute walk distance and Borg dyspnoea scale
- WHO functional class
- NT-proBNP
- Quality of life (CAMPHOR questionnaire) and the self-reported Patient Global Assessment
- Safety - the occurrence of adverse events
- Cardiac MRI - right ventricular volumes, mass, ejection fraction, stroke volume and diastolic function. Details are described in the SPM.

## **4. INVESTIGATIONAL PLAN**

### **4.1. Overall study design and plan**

This study is a Phase II, multicentre, double-blind, randomised, placebo-controlled, crossover study.

The study consists of a screening process, two treatment periods at Week 0 and Week 12 plus a follow up phase to evaluate the kinetics of iron re-depletion.

Potential participants will be screened using data collected during their routine outpatient appointment at the Pulmonary Hypertension Service or PH Clinic. Any unavailable or missing data will be collected at the screening visit (week 0) once the patient has provided written informed consent.

The study will involve hospital visits at Weeks 0, 12 and 24 while participants will be followed up by telephone on week 2 and 14.

Eligible participants will be admitted to the research unit for up to 3 days in order to complete the Baseline (Week 0) assessments including a physical examination, medical history, ECG, bloods to assess routine haematology and clinical chemistry and measure biomarkers, 6-Minute Walk Test, CAMPHOR questionnaire and incremental and endurance cardiopulmonary exercise tests (CPET).

As outlined in Figure 1, following completion of the Baseline assessments at Week 0 patients will be randomly allocated 1:1 to receive an infusion of either Ferinject® or saline.

At Week 2 participants will receive a telephone call from the research unit for follow up. This will include a general assessment of AEs, other medication and PGA questionnaire.

At Week 12 participants will be admitted to the research unit for up to 3 days to repeat the assessments done at Baseline (Week 0). Following completion of the Week 12 procedures, the patients will be switched to the other treatment arm (i.e. those who received Ferinject® at baseline will be administered a saline infusion, and vice versa).

Thereafter participants will have follow up assessments by telephone at Week 14 (which will be the same as week 2) and a final hospital visit at week 24 (which will be the same as the Weeks 0 and 12 visits)

At the sites where facility is available, participants will be given the option to undergo additional cardiac MRI (Weeks 0, 12 and 24).

At the Sheffield site only, if participants agree, at each of the week 0 and week 12 visits they will have two extra blood samples taken (50 ml extra in total) to assess neutrophil and peripheral blood mononuclear cell function and expression.

#### **4.2. Discussion of study design**

Patients will be randomised 1:1 to Ferinject® or saline, with a 6-minute walk test, cardiac MRI and incremental and endurance cardiopulmonary exercise tests to measure changes in cardiopulmonary performance. Patients will then receive the alternative treatment and 6-minute walk test and endurance and incremental cardiopulmonary exercise testing repeated after a further 12 weeks (Figures 1). This crossover design maximises the data available on exercise testing at 12 weeks post-iron for analysis.

#### **4.3. Selection of Study Population**

Patients participating in this study are adult males and females with symptomatic IPAH as defined by the eligibility criteria below.

##### **4.3.1. Inclusion criteria:**

Eligible patients must meet all of the following inclusion criteria:

1. Males or females aged between 16–75 years old.
2. PAH which is idiopathic, heritable or associated with anorexigens.
3. Iron deficiency as defined by any one of the following criteria: sTfR levels > 28.1 nmol/l (where sTfR analysis is available) or one of the following: ferritin <37 µg/l; transferrin saturations <16.4%; iron < 10.3 µmol/l.

4. Documented diagnosis of PAH by right heart catheterisation performed at any time prior to Screening showing: resting mean pulmonary artery pressure >25mmHg, pulmonary capillary wedge pressure =/≤ 15 mm Hg and normal or reduced cardiac output.
5. 6 minute walking distance greater than 50m at entry.
6. Stable on an unchanged PAH therapeutic regime (any combination of endothelin receptor antagonist, phosphodiesterase inhibitor or prostacyclin analogue) for at least 1 month.
7. Able to provide written informed consent prior to any study-mandated procedures.
8. Female subjects of child-bearing potential are eligible to participate if they agree to use one of the following contraception methods:
  - combined (estrogen and progestogen containing) hormonal contraception associated with inhibition of ovulation:
    - oral
    - intravaginal
    - transdermal
  - Progestogen-only hormonal contraception associated with inhibition of ovulation:
    - oral
    - injectable
    - implantable
  - intrauterine device (IUD)
  - intrauterine hormone-releasing system (IUS)
  - bilateral tubal occlusion
  - vasectomised partner
  - sexual abstinence

#### **4.3.2. Exclusion criteria:**

Patients will not be enrolled into the study if they meet any of the following criteria:

1. Unable to provide informed consent.
2. Clinically-significant renal disease (Creatinine clearance < 30 ml/min per 1.73 m^2 calculated from CKD-Epi <http://www.qxmed.com/renal/Calculate-CKD-EPI-GFR.php>) or liver disease (including serum transaminases > 3 times upper limit of normal).
3. Haemoglobin concentration <10 g/dl.
4. Patients will be excluded if any single parameter (iron, ferritin or transferrin saturation) exceeds 1x upper limit of normal (ULN) in the local lab reference range.
5. Patients with moderate to severe hypophosphatemia as defined as <0.65mmol/L
6. Known to have haemoglobinopathy e.g. sickle cell disease, thalassaemia.
7. Admission to hospital related to PAH or change in PAH therapy within 1 month prior to Screening.
8. Evidence of left ventricular disease or significant lung disease on high-resolution CT scanning or lung function as judged by the investigator.
9. Acute or chronic infection or inflammation.
10. Significant uncontrolled asthma as judged by the investigator, eczema or atopic allergies.
11. Females who are lactating or pregnant.
12. Individuals known to have HIV, Hepatitis B or C or Creutzfeld-Jakob disease.
13. Known hypersensitivity to Ferinject® or any of its excipients and any other iron preparations.
14. Evidence of disturbances in utilisation of iron.
15. Significant blood loss (e.g. GI bleed) within the last 3 months or history of menorrhagia.

16. Unable to perform a Cardiopulmonary Exercise Test i.e. due to syncope or musculoskeletal factors.
17. Patients who have received an investigational medicinal product within 30 days of entering the baseline visit.

#### **4.3.3. Subject Completion**

Subjects will be considered complete for the purpose of this study once they have completed all procedures at the end of Week 24.

The end of study is defined as the last visit of the last subject undergoing the trial.

#### **4.3.4. Withdrawal of Subjects from Study**

Patients will be informed that they have the right to withdraw from the study at any time for any reason, without prejudice to their medical care. The investigator can withdraw subjects from the study for any of the following reasons:

- Occurrence of an unacceptable adverse event
- Subject request
- Subject is lost to follow up
- Administrative reasons
- Development of an intercurrent illness, condition, or procedural complication, which would interfere with the subject's continued participation
- Patient becomes pregnant

The investigator also reserves the right to withdraw subjects in the interest of subject safety and welfare.

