#### **4.3.5. Replacement policy**

Patients who are prematurely discontinued from the study will not be replaced.

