# 8. PHARMACOVIGILANCE

## 8.1. Definitions

**Adverse Event (AE):** any untoward medical occurrence in a patient or clinical trial subject administered a medicinal product and which does not necessarily have a causal relationship with this treatment. *An AE can therefore be any unfavourable and unintended sign (including an abnormal laboratory finding), symptom, or disease temporally associated with the use of an investigational medicinal product (IMP), whether or not considered related to the IMP.*

**Adverse Reaction (AR):** all untoward and unintended responses to an IMP related to any dose administered. *All AEs judged by either the reporting investigator or the sponsor as having reasonable causal relationship to a medicinal product qualify as adverse reactions. The expression reasonable causal relationship means to convey in general that there is evidence or argument to suggest a causal relationship.*

**Unexpected Adverse Reaction:** an AR, the nature or severity of which is not consistent with the applicable product information (e.g. investigator's brochure for an unapproved investigational product or summary of product characteristics (SmPC) for an authorised product). *When the outcome of the adverse reaction is not consistent with the applicable product information this adverse reaction should be considered as unexpected. Side effects documented in the SmPC which occur in a more severe form than anticipated are also considered to be unexpected.*

**Serious Adverse Event (SAE) or Serious Adverse Reaction (SAR):** any untoward medical occurrence or effect that at any dose:

- Results in death
- Is life-threatening
- Requires hospitalisation, or prolongation of existing inpatients' hospitalisation
- Results in persistent or significant disability or incapacity
- Is a congenital anomaly or birth defect

Medical judgement should be exercised in deciding whether an AE/AR is serious in other situations. Important AE/ARs that are not immediately life-threatening or do not result in death or hospitalisation but may jeopardise the subject or may require intervention to prevent one of the other outcomes listed in the definition above, should also be considered serious.

**Suspected Unexpected Serious Adverse Reaction (SUSAR):** any suspected adverse reaction related to an IMP that is both unexpected and serious.

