## **8.8. Follow up of adverse events**

All adverse events that are still ongoing at the end of the study will be followed up until resolution.

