# **10. STATISTICS AND DATA ANALYSIS**

This is a proof-of-concept study, thus the sample size has been chosen with respect to safety (in terms of exposure to the drug and investigations) and feasibility (patient population) and with the aim of measuring effect size. We would expect that a sample size of 60 will be sufficient to detect clinically meaningful changes in cardiopulmonary exercise end-points, NT-pro-BNP and quality of life in the direction consistent with benefit.

The null hypothesis is that iron replacement has no effect on cardiopulmonary performance in patients with iron deficiency and IPAH, with a two-sided alternative that iron replacement changes cardiopulmonary performance in patients with iron deficiency and IPAH.

For the cardiopulmonary exercise tests, if a 12-weekly drop-out rate of 10% and standard deviation of 5 ml/min/kg for peak VO2 we would have 80% power to detect a mean change of 1.94 ml/min/kg at a significance level of alpha=0.05 using a paired analysis (cf 2.2ml difference in FERRIC-HF with 35 patients). Other pre-specified secondary endpoints will be change in CPET at 2 weeks, change in cardiac output at 12 weeks, and change in 6 minute walk distance and circulating biochemical markers at 12 weeks. A full statistical analysis plan will be developed for each endpoint, using linear mixed models for analysis of the crossover data. Primary analysis will be intention-to-treat, with sensitivity analyses to explore the effect of dropout. Due to the exploratory nature of the study no multiplicity adjustment will be made to p-values for secondary analyses, though results will be interpreted with caution if the primary endpoint does not achieve significance.

It will only be possible to measure sTfR for every study participant after enrolment and thus a separate analysis will be performed to analyse the effect of Ferinject® in patients with sTfR > 28.1 nmol/l. Additionally, on recruitment of the 20th, 40th and 60th patient, serum samples will be analysed to establish the number of patients enrolled with sTfR > 28.1 nmol/l and an additional number of patients will be recruited to achieve 60 enrolled iron-deficient patients.

Data from all centres will be pooled and analysed at Hammersmith. Due to the small sample sizes in each centre, the assessment of consistency of results amongst the centres will be made on an informal basis.

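### The protocol allows withdrawal from the study for adverse events, intercurrent illness or pregnancy but defines no status of no further infusion with follow-up continuing, so outcome and safety data can be lost needlessly

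*Protocol*

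**What the plan says.** Protocol section 4.3.4 states that "The investigator can withdraw subjects from the study for any of the following reasons". Among the reasons are "Occurrence of an unacceptable adverse event", "Patient becomes pregnant" and an intercurrent illness that would interfere with taking part. Section 4.3.5 adds that "Patients who are prematurely discontinued from the study will not be replaced".

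Other sections bear on what a withdrawal costs:

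- Section 5.2.2: each patient has a single iron infusion, at Week 0 or Week 12. By section 4.1, saline is given at the other visit.
- Sections 6.5 and 6.6: after Week 12 dosing, a telephone call at Week 14 and a visit at Week 24 remain.
- Section 1: all patients are to be followed for up to 24 weeks after iron.
- Section 3.2: the occurrence of adverse events is a secondary outcome.
- Section 10: "Primary analysis will be intention-to-treat, with sensitivity analyses to explore the effect of dropout". Linear mixed models are planned for the crossover data.
- Section 6, opening text: a patient may forgo an investigation and stay in the study. Forgoing an infusion is not mentioned.
- Section 8.8: "All adverse events that are still ongoing at the end of the study will be followed up until resolution". Section 4.3.3: "The end of study is defined as the last visit of the last subject undergoing the trial".
- Section 8.1 lists among the serious criteria: "Is a congenital anomaly or birth defect".

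**The concern.** Stopping study treatment and stopping data collection are different decisions, and the protocol has words only for the second. In a trial of repeated dosing, withdrawal at least ends exposure. Here treatment is one infusion per period. A patient with an unacceptable event after the first infusion has only the Week 12 infusion left to omit, and a patient in the second period has nothing left to omit.

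Two results are at stake. The first is the treatment comparison. An intention-to-treat analysis needs outcomes after an adverse event as much as before it, and each withdrawn patient is unreplaced. The second is the adverse event outcome, because the patients whose harm most needs observing are those for whom the protocol offers an exit without saying what is collected afterwards.

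**Working it through.** **1. What each exit removes (from sections 4.1, 5.2.2 and 6.3 to 6.6).**

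| Time of exit | Study treatment left to omit | Data lost | What retention would restore |
|---|---|---|---|
| Between Week 0 and Week 12 | Week 12 infusion | Week 2 call if not yet made; Week 12 outcome; all later contacts | Week 12 outcome and safety data; no within-patient contrast if the second infusion is not given |
| After Week 12 dosing | None | Week 14 call if not yet made; Week 24 outcome | Second half of the within-patient contrast, and safety data |

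The second row is the clearest cost: treatment is complete and only information is lost.

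**2. The plan's own figure and its dropout allowance (section 10).** Inputs: 60 patients, 10% dropout per 12 weeks, SD 5 ml/min/kg for peak VO2, two-sided alpha 0.05, 80% power, paired analysis. The SD is assumed to be that of the paired difference. Power is the chance that a noncentral t variable with n − 1 degrees of freedom and noncentrality (1.94/5) × √n falls outside ± t(0.975, n − 1).

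- 60 × 0.9 = 54 pairs: detectable difference 1.942, power at 1.94 is 79.9%. The stated 1.94 is reproduced, with dropout counted once.
- 60 × 0.9 × 0.9 = 48.6 pairs, the same rate in both periods: power 75.0% (48 pairs) or 75.9% (49 pairs), detectable difference 2.06 or 2.04.

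Lost pairs therefore matter. This figure concerns peak VO2, a secondary outcome. Section 10 gives no SD for endurance time, the primary outcome.

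**3. How many iron-exposed patients could have shortened follow-up.** Assume equal sequences (30 and 30), the planned dropout rate in each period, and that everyone reaching Week 12 is dosed.

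- Period 1 leavers: 60 × 0.10 = 6, of whom 3 had iron first.
- Period 2 leavers: 54 × 0.10 = 5.4, all iron-exposed by then.
- Iron-exposed in total: 30 + 27 = 57.
- Shortened follow-up: 3 + 5.4 = 8.4, and 8.4/57 = 14.7%.

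Of the 5.4, half (2.7) had iron first and already have 12 weeks of data after it. Those lost within 12 weeks of iron number 3 + 2.7 = 5.7, and 5.7/57 = 10%. Both figures count every cause of dropout.

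**4. Bias.** The protocol gives no exit rate by reason or by treatment, so the bias cannot be computed. By assumption only: if a share f is lost and its unseen treatment difference departs from that of completers by k, a completers-only estimate is off by f × k. For f from 0.05 to 0.19 (1 − 0.81, all causes) and k from 1 to 2 ml/min/kg, that is 0.05 to 0.38 ml/min/kg, or 3% to 20% of 1.94. The planned analysis is a mixed model, so this shows scale and does not predict a result.

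**5. Whether section 8.8 closes the gap.** Read with section 4.3.3, the end of the study is a date for the whole trial. The planned dates in the Study Summary (first visit Q4 2011, last visit Q4 2017) put it up to about six years after an early exit. An event that began before exit and is still ongoing at that date is covered. An event that begins after exit is not covered, and nothing is specified for the interval between exit and study end.

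**6. Pregnancy.** Table 1 schedules tests at Weeks 12 and 24, so a pregnancy may be found after iron exposure. Section 8 contains no reporting of pregnancy or its outcome, although section 8.1 treats a congenital anomaly as serious.

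**The case against.** The strongest reply is that section 4.3.4 is permissive. A reader might infer that these events force patients out. The text does not say so: the investigator may withdraw a patient, and nothing forbids keeping one. This stands, and it limits the point to what the protocol permits and fails to define.

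A reader might also infer that bias is established. It is not. Bias needs exit related to treatment or outcome and not handled by the analysis, and section 10 plans mixed models and dropout sensitivity analyses. These help if data are missing at random. They cannot recover uncollected data, and exit because of an adverse event is a case where that assumption is doubtful.

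A third tempting reading is that an event ongoing at early exit has no follow-up at all. Section 8.8 is not limited to enrolled patients and literally covers such an event if it persists to study end. Section 8.4.2.2 also requires prompt reporting of further information on a known serious event, with no exception for withdrawn patients, though it creates no duty to seek that information. The gap is narrower: new events, and the interval.

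Finally, keeping a pregnant patient to Week 24 would generally not reveal a congenital anomaly. That gap comes from the missing pregnancy-outcome reporting and not from the withdrawal rule.

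**Conclusion.** The point holds as a weakness in a stated rule. The only written response to an unacceptable adverse event, intercurrent illness or pregnancy is an optional exit from the whole study. After Week 12 dosing that exit stops no treatment and costs the Week 14 and Week 24 data. In the first period it can cost the Week 12 outcome and later adverse event data. The rule fits poorly with sections 1, 3.2 and 10.

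Bias in the comparison and in the safety data is possible, of unknown size. The 8.4 of 57 (15%) should not be read as the effect of this rule. It is an all-cause ceiling at the planning rate, it includes refusals and losses that no wording would prevent, and it rests on equal sequences and full dosing at Week 12. Who stays in follow-up is a protocol rule, so a statistical analysis plan could not repair it. The change is inexpensive and should be made.

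**What to change.** - **Section 4.3.4:** define two statuses, no further study infusion and withdrawal from follow-up. State that, unless consent is withdrawn or the patient is lost, adverse event collection and the scheduled Week 2, 12, 14 and 24 contacts continue, with only those assessments the investigator judges suitable. The opening of section 6 already allows tests to be skipped.
- **Section 8.8:** refer to the subject's last visit or early exit in place of the end of the study.
- **Section 8:** add reporting of pregnancy outcome to the sponsor.
- Reconcile sections 1, 4.3.4, 8.8 and 10 with these changes.

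Whether an infusion or an exercise test is given remains a clinical decision, and nothing here prescribes it.

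The cost is protocol and consent wording, visits already in the schedule, and the added pregnancy reporting. The gain is partial. Some patients will decline, and a patient who misses the second infusion contributes first-period and safety data but no within-patient contrast.
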